9.3 Serious Adverse Event Reporting

An event that is serious must be recorded on the source document and requires expeditious handling to comply with regulatory requirements.

- **Reporting to IRB:** In accordance with the standard operating procedures and policies of the local Institutional Review Board (IRB)/Independent Ethics Committee (IEC), the site investigator will report SAEs to the IRB as soon as possible but not later than 7 days after first knowledge by investigator.
- **Reporting to Flexion:** All serious adverse events in patients treated with Zilretta must be reported to Flexion within 3 calendar days. The Investigator should attempt to collect as much information about the adverse event as needed to get a complete medical understanding. Any new information collected on an SAE should be forwarded to Flexion as it becomes available.

9.4 Reporting to the US FDA

All serious adverse events which are considered causally related to Zilretta must be assessed for whether it is expected per the Investigators Brochure. An unexpected event means that it is not described within the reference safety information (the Zilretta IB) as associated with Zilretta.

If an event is assessed as serious, related to Zilretta, and unexpected, it must be reported to the FDA according to 21CFR312.32.

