BACKGROUND/ RATIONALE	Zilretta is approved for intra-articular injection into the knee joint for treatment of osteoarthritis (1). There are ongoing studies for intra-articular injection into the other large joints including the shoulder and hip joints (2). To our knowledge, there has been no prior study to prove efficacy of injection of the extended release steroid into the bursa. The bursae surrounding the hip joint including the iliopsoas and the greater trochanteric bursa are some of the larger bursae in the body. Conventional treatment for inflammation of these bursae is injection of corticosteroids (3). We believe that a long acting corticosteroid, if efficacious, can have a great impact. There is a significant population of patients suffering from chronic bursal pain, who might benefit. At our institute, bursal injection of the steroid in the region of hips is one of the most common locations, second to joint injections. To our understanding, the bursa surrounding the hip are deep enough to avoid side effects associated with subcutaneous injection of steroid. The current proposal is a pilot study.
STUDY DESIGN	This is a prospective, open-label, pilot study, to assess the safety and efficacy of FX006 (triamcinolone acetonide extended release injectable suspension 32 mg) , administered to patients with greater trochanteric bursitis.
PRIMARY OBJECTIVE	The primary objective will be to determine the safety and efficacy of this drug in bursal injections by monitoring the improvement in the pain from baseline, as established using the using a Numeric Pain Rating Scale (NPRS) score at the end of 12 weeks.
SECONDARY OBJECTIVES	Secondary objective is to determine any alteration in the Patient Global Impression of Change (PGIC) measure. This is used as an indicator to assess the patient's impression to change in treatments, to their chronic pain.
PRIMARY END POINT	The primary endpoint will be the improvement in the pain from baseline, at the end of week 12, as determined by the NPRS pain score
SECONDARY END POINT	The secondary endpoint will be any alteration in the PGIC measure, at the end of week 12.

NUMBER OF SUBJECTS

24 patients

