4.3 Safety Evaluations

Incidence of adverse events will be recorded and reported to appropriate bodies including the UTHealth IRB and FDA, if indicated.

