9.2 Definitions

Adverse Event (AE): Any untoward medical occurrence in a clinical investigation of a patient administered a pharmaceutical product and that does not necessarily have a causal relationship with the treatment. An AE is therefore any unfavorable and unintended sign (including an abnormal laboratory finding), symptom or disease temporally associated with the administration of an investigational product, whether or not related to that investigational product. An unexpected AE is one of a type not identified in nature, severity, or frequency in the current Investigator's Brochure or of greater severity or frequency than expected based on the information in the Investigator's Brochure.

Serious Adverse Event (SAE): An SAE is any untoward medical occurrence that at any dose:

- Results in death,
- Is life-threatening, ("Life-threatening" refers to an event in which the patient was at substantial risk of death at the time of the event; it does not refer to an event which hypothetically might have caused death if it were more severe.)
- Requires inpatient hospitalization or prolongation of existing hospitalization,
 - Note: Adverse events requiring hospitalizations that are less than 24 hours in duration generally do not meet this criterion. A scheduled hospitalization for an elective procedure or a pre-existing condition that has not worsened during participation in the

study does not meet this criterion.

- Results in permanent or significant disability/incapacity; a substantial disruption of the patient's ability to carry out normal life functions.
- Is a congenital anomaly/birth defect.
- Is an important medical event: event that may not be immediately life-threatening or result in death or hospitalization but may jeopardize the patient or may require intervention to prevent one of the outcomes listed in the definition above.

Severity: the intensity of the adverse event. This is not the same as "serious," which is based on patient/event outcome or action criteria usually associated with events that pose a threat to a patient's life or functioning. The severity of AEs will be assessed according to the following definitions:

Table 1: AE Severity Grading

Severity	Description
Mild	The AE is noticeable to the patient and/or the Investigator, but does not interfere with routine activity.
Moderate	The AE interferes with routine activity, but responds to symptomatic therapy or rest.

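### Sections 9.2 and 9.4 define an unexpected event differently, and the narrower definition decides FDA reporting, so a serious related event worse than the brochure describes could go unreported to the FDA

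*Combined protocol and SAP*

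**What the plan says.** Section 9.2 (Definitions) gives a definition in two limbs. The first is "An unexpected AE is one of a type not identified in nature, severity, or frequency in the current Investigator's Brochure". The second, joined by *or*, adds an event "of greater severity or frequency than expected based on the information in the Investigator's Brochure".

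Section 9.4 (Reporting to the US FDA) requires serious events considered causally related to Zilretta to be checked for expectedness against the brochure. It then supplies its own definition: "An unexpected event means that it is not described within the reference safety information (the Zilretta IB) as associated with Zilretta". The reporting trigger follows directly: "If an event is assessed as serious, related to Zilretta, and unexpected, it must be reported to the FDA according to 21CFR312.32".

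Three other places bear on the point:

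- Section 4.3: "Incidence of adverse events will be recorded and reported to appropriate bodies including the UTHealth IRB and FDA, if indicated".
- Section 9.3: "the site investigator will report SAEs to the IRB as soon as possible but not later than 7 days after first knowledge by investigator". The same section requires all serious adverse events to go to the manufacturer (Flexion) within 3 calendar days. Neither route depends on expectedness.
- Section 14.5, item 12, commits the investigator to the other pertinent requirements of 21 CFR part 312.

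**The concern.** Under Section 9.4 an event goes to the FDA only if it is serious, related and unexpected. Expectedness is the last of these conditions, so its definition settles the outcome for any event that has met the first two. The same facts can therefore give opposite decisions depending on which section the assessor opens, and someone deciding on an FDA report will naturally open the section with that title.

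The affected class is not far-fetched. The causality table in Section 9.2 explains *related* partly by consistency with what is already known of the product or its class. Events judged related will therefore tend to be of known types, and for known types the severity and frequency limb is what keeps a worse-than-described event reportable. Section 9.4 omits that limb.

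Safety is part of the primary objective (Section 2.1), and Section 12 expects the pilot to help establish it. The product is being used outside the setting the protocol gives for its approval: "Zilretta is approved for intra-articular injection into the knee joint for treatment of osteoarthritis". A rule for recognising known reactions in a worse form should therefore be unambiguous.

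**Working it through.** The plan gives no figure here and no arithmetic applies to the contradiction itself. The check is to apply both definitions to every kind of event that can reach the expectedness step, namely a serious event already judged related.

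| Serious, related event | Section 9.2 | Section 9.4, read literally | FDA report |
|---|---|---|---|
| (a) Type not described in the brochure | Unexpected | Unexpected | Yes under both |
| (b) Type described, at the same severity and frequency | Expected | Expected | No under both |
| (c) Type described, but the event is more severe or more frequent than described | Unexpected | Expected | Yes under 9.2, no under 9.4 |

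1. The sections agree in (a) and (b). They disagree only in (c).
2. The disagreement in (c) comes from the wording. The second limb of 9.2 has no counterpart in 9.4. The verb in 9.4 is *means*, so its sentence reads as a definition and not as an example.
3. Nothing in 9.4 refers to 9.2, and nothing in either section says which prevails.
4. The conflict is separate from the causality judgement, because every row concerns an event already accepted as related.
5. Outside the FDA route, (c) is still reported: Section 9.3 sends it to the manufacturer within 3 calendar days and to the IRB within 7 days. The documents do not say that either recipient would pass it to the FDA.

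The two parts of the omitted limb do not carry equal weight. One event can show greater severity than described. One event cannot establish greater frequency in a study of this size. One case among the 24 planned subjects is 1/24 = 4.2%. If the true rate were 1% (an assumption; the brochure's rates are not in the documents), the chance of at least one case would be 1 − 0.99^24 = 21%. At an assumed 0.1% it would be 1 − 0.999^24 = 2.4%. The practical weight of the point therefore rests mainly on severity.

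**The case against.** The strongest reply is that the protocol, read as a whole, still captures these events. The broader definition stands in the section headed Definitions, and 9.4 does not disapply it. Section 9.4 ties reporting to 21CFR312.32, Section 14.5 binds the investigator to part 312, and Section 4.3 provides for FDA reporting where indicated. An assessor might also treat an event much worse than the brochure's account as not described there at all, which would bring 9.4 close to 9.2.

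This limits the consequence but does not remove the contradiction. That 9.2 also stands is one half of the conflict. Section 4.3 gives no criterion for when a report is indicated. The regulation is cited for how to report an event already assessed as unexpected, and for that assessment 9.4 provides its own test. The regulation's text is not in the documents, and nothing here relies on it.

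The objection does defeat three stronger inferences that a reader might draw:

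- *Such events would not be reported to the FDA.* The documents support only that they could go unreported if 9.4 is applied literally and alone.
- *A serious bursal reaction would be lost.* This depends on a brochure that is not available here. If the brochure does not describe the reaction, which is possible given that the protocol presents bursal injection as new, the event falls in row (a) and is reported under both sections. The IRB and the manufacturer would receive it in any case.
- *The gap can be expressed as a multiple of the brochure rate.* Any such multiple would rest on assumed rates and on a single case that cannot show an excess.

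**Conclusion.** The point holds as an internal contradiction with a limited but real consequence. Sections 9.2 and 9.4 cannot both govern expectedness, and the narrower one sits at the FDA trigger. One class of event is affected: serious, judged related, of a type the brochure describes, and more severe or more frequent than described. For that class the FDA decision reverses according to the section used.

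How many events this would involve cannot be stated, because the brochure's listed types, severities and rates are not in the documents. In a study of 24 subjects the number is likely to be small, possibly none. The conclusion rests on reading 9.4 by its plain words. It needs no assumption about the brochure beyond its describing at least one reaction that could occur in a more serious form. The amendment should be made because a stated rule, followed as written, would class as expected an event that the protocol's own Definitions section calls unexpected.

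**What to change.** Delete the definition sentence in Section 9.4 and replace it with a reference to Section 9.2. For example: *Expectedness is assessed using the definition of an unexpected adverse event in Section 9.2, which includes events of greater severity or frequency than the Investigator's Brochure describes.* Leave the trigger sentence and its regulatory citation unchanged, so that one definition governs FDA reporting.

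No separate rule comparing bursal with intra-articular events is needed, since the 9.2 definition already requires comparison on severity and frequency.

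The cost is one sentence in a protocol amendment. The small downside is that a few more events may need FDA reports. Data collection, sample size and the planned analyses do not change.

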9.5 Pregnancy

All pregnancies, female patients or female partners of male patients during the study, must be evaluated by the Investigator and/or other medically qualified personnel. The Investigator must continue to follow the pregnancy until the completion of the pregnancy, including the outcome and the condition of the newborn (if applicable). Additional subsequent follow-up is not needed when a newborn baby is healthy. Information on the pregnancy, including follow up reports, and any data on the birth of the newborn should be reported to Flexion within 3 days.

10 DISCONTINUATION AND REPLACEMENT OF SUBJECTS

10.1 Early Discontinuation of Study Drug

A subject may be discontinued from study treatment at any time if the subject, the investigator, or Flexion Therapeutics, Inc. feels that it is not in the subject's best interest to continue. The following is a list of possible reasons for study treatment discontinuation:

Subject withdrawal of consent (or assent)

Subject is not compliant with study procedures

Adverse event that in the opinion of the investigator would be in the best interest of the subject to

discontinue study treatment

Protocol violation requiring discontinuation of study treatment

Lost to follow-up

Flexion Therapeutics, Inc. request for early termination of study

If a subject is withdrawn from treatment due to an adverse event, the subject will be followed and treated by the Investigator until the abnormal parameter or symptom has resolved or stabilized.

All subjects are free to withdraw from participation at any time, for any reason, specified or unspecified, and without prejudice.

Reasonable attempts will be made by the investigator to provide a reason for subject withdrawals. The reason for the subject's withdrawal from the study will be specified in the subject's source documents. Refer to Section 10 for early termination procedures.

10.2 Withdrawal of Subjects from the Study

A subject may be withdrawn from the study at any time if the subject, the investigator, or the Sponsor feels that it is not in the subject's best interest to continue.

All subjects are free to withdraw from participation at any time, for any reason, specified or unspecified, and without prejudice.

Reasonable attempts will be made by the investigator to provide a reason for subject withdrawals. The reason for the subject's withdrawal from the study will be specified in the subject's source documents.

10.3 Replacement of Subjects

Subjects who withdraw from the study treatment will be replaced.

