9 ADVERSE EXPERIENCE REPORTING AND DOCUMENTATION

9.1 Collection

Adverse events will be collected from the time of medication administration until completion of the follow-up telephone calls at week 12 or until subject participation in study ends.

The Investigator or other medical trained personnel will probe, via discussion with the subject, for the occurrence of Adverse Events during each subject contact and record the information in the source documents. Adverse events will be recorded in the patient CRF. Adverse events will be described by duration (start and stop dates and times), outcome, and treatment. The Investigator, or other medical trained personnel will also assess the seriousness and severity of the event, and relationship of the event to study drug according to the definitions below. If unrelated to study drug, the more likely cause of the event will also be assessed and recorded.

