14.3 Informed Consent Form

Informed consent will be obtained in accordance with the Declaration of Helsinki, ICH GCP, US Code of Federal Regulations for Protection of Human Subjects (21 CFR 50.25 [a,b], CFR 50.27, and CFR Part 56, Subpart A), the Health Insurance Portability and Accountability Act (HIPAA, if applicable), and local regulations.

The Investigator will send an IRB-approved copy of the Informed Consent Form to Flexion Therapeutics, Inc.

A properly executed, written, informed consent will be obtained from each subject prior to entering the subject into the trial. Information should be given in both oral and written form and subjects must be given ample opportunity to inquire about details of the study. If a subject is unable to sign the informed consent form (ICF) and the HIPAA authorization, a legal representative may sign for the subject. A copy of the signed consent form (and assent) will be given to the subject or legal representative of the subject and the original will be maintained with the subject's records.

Pending IRB approval, a research nurse may obtain informed consent remotely including means such as phone, video or other verbal means for the purposes of screening a trial subject. Written informed consent shall be obtained prior to the subject entering the trial

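### Do the replacement rule and the missing efficacy set leave the Week-12 NPRS result undefined?

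*Combined protocol and SAP*

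**What the plan says.** Sections 7.2.1 and 7.2.3 give FX006 once per subject, and Section 7.1 puts the number injected at 24. Section 10.3 is a single sentence: "Subjects who withdraw from the study treatment will be replaced". It does not say whether it applies before the injection, after it, or both.

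Section 10.1 introduces its reasons with "The following is a list of possible reasons for study treatment discontinuation". Among them are an adverse event ("Adverse event that in the opinion of the investigator would be in the best interest of the subject to" discontinue) and "Lost to follow-up". It ends with "Refer to Section 10 for early termination procedures", although it is itself part of Section 10, which lists no assessments for that point. Section 10.2 deals separately with leaving the study ("A subject may be withdrawn from the study at any time") and has no replacement rule. Both sections require the reason for withdrawal to be kept in the source documents.

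The primary endpoint (Section 4.1) is NPRS improvement from baseline at Week 12. Section 12 derives the sample size from patient availability over 6 months, and plans summary statistics for NPRS and PGIC at each time point and their change over time. Section 12.1 defines only a safety population. No section defines an efficacy set or a missing-data rule.

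**The concern.** After a single injection there is no study treatment left to withdraw from, so Section 10.3 would seem to concern only people who leave between consent and injection. Section 10.1 blurs that reading. It counts adverse events as a reason for stopping study treatment, and Section 9.1 says "Adverse events will be collected from the time of medication administration until completion of the follow-up telephone calls at week 12". Loss to follow-up also belongs naturally to the telephone calls after Day 1. Read this way, Section 10.3 could replace injected subjects and take the number injected above 24.

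Two consequences would follow. More people would be exposed than Section 7.1 states. The efficacy n would also return to 24, so that losses were less obvious beside the primary result. With no efficacy set and no missing-data rule, the Week-12 figure could then rest on those who stayed, while Section 12 intends the data for planning a later efficacy trial.

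**Working it through.** **The plan's own figure.** N = 24 cannot be reproduced by a formula and is not meant to be. Section 12 bases it on availability and gives no SD, effect size, power or dropout rate. All inputs below are therefore assumptions: dropout d of 10% or 20%, SD of 2 to 3 points, and a gap of 1 to 3 points in mean improvement between completers and leavers.

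**Step 1: number injected, if injected leavers were replaced.**
- One round, 24(1 + d): 24 × 1.1 = 26.4 (5th to 95th percentile 24 to 29); 24 × 1.2 = 28.8 (26 to 32).
- Repeated until 24 complete, 24/(1 − d): 24/0.9 = 26.7 (24 to 30); 24/0.8 = 30.0 (26 to 35).
- Without replacement, 24(1 − d) have a Week-12 score: 21.6 (19 to 24) and 19.2 (16 to 22).

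**Step 2: does replacement bias the Week-12 mean?** Simulated improvement is normal with mean 2 and SD 2.5, over 40,000 trials, with logistic dropout of slope 0.5 per point. Completer means, without and with replacement:

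| Who leaves | 10% dropout | 20% dropout |
|---|---|---|
| Poor responders | 2.27 / 2.27 | 2.51 / 2.50 |
| Unrelated to response | 2.01 / 2.00 | 2.00 / 2.00 |
| Good responders | 1.73 / 1.73 | 1.49 / 1.49 |

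Each pair agrees to within 0.01. The departure from 2.00 comes from who is missing, not from replacement.

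**Step 3: size of the missing-data effect.** Bias of the completer mean = d × gap. The smallest is 0.10 × 1 = 0.1 and the largest 0.20 × 3 = 0.6, and the sign is unknown. At n = 24 the standard error is 2/√24 = 0.41 to 3/√24 = 0.61. Without replacement at 20% dropout and SD 2 it is 2/√19.2 = 0.46, so the largest bias is 0.6/0.46 = 1.3 standard errors. The higher ratio 0.6/0.41 = 1.5 needs n restored to 24, which is the disputed reading of Section 10.3.

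**Step 4: would a prescribed rule do better?** The obvious candidate scores a missing Week-12 value as no improvement. In the same simulation (true mean 2.00):

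| Who leaves | 10% dropout | 20% dropout |
|---|---|---|
| Poor responders | 2.04 | 2.01 |
| Unrelated to response | 1.80 | 1.60 |
| Good responders | 1.55 | 1.19 |

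It helps only in the first row. At 20% dropout that is because a mean of 2.0 happens to place the simulated leavers near zero improvement. With a mean of 3.0 and the same model, leavers average about 0.97 and the summary is about 0.20 × 0.97 = 0.19 too low. In the other two rows it is further from the truth than the observed mean.

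**Step 5: what the text already supplies.** Section 12 asks for summaries at each time point, which for a descriptive report means the scores observed then. A leaver's earlier scores count at their own calls. Section 3.1 schedules calls at Weeks 1, 2, 4, 8 and 12 for all patients, and no passage stops them for someone who stays in the study. The safety denominator and the withdrawal reasons would show a loss even if the efficacy n returned to 24.

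**The case for a change.** The strongest case for a change is that it would cost a few sentences and settle the denominator before results are seen. Week-12 NPRS is the primary endpoint, the result feeds a later trial, and two coordinators could apply Section 10.3 differently.

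Part of this stands. Section 10.3 is loose. Section 10.1 uses the term study treatment in a way that can reach injected subjects, and its pointer to Section 10 is circular. Section 12.1 is also careless: it refers to eligible, randomized patients in a single-arm study. Taken literally, it might leave out an injected subject later found ineligible. That is a slip of wording which matters only if such a subject is injected.

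The rest carries less weight. The reading limited to withdrawal before injection has good support: one administration, 24 to be injected, a separate section on leaving the study with no replacement rule, and time between consent and injection in which someone can change their mind. Section 14.3 widens that interval, since, pending IRB approval, "a research nurse may obtain informed consent remotely" for screening. The reasons in Section 10.1 are a generic list of possibilities. A last score at withdrawal, reported apart from Week 12, would leave the Week-12 result as it is. Nothing in the plan prescribes a completers-only claim.

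**Conclusion.** No change follows. The omissions are real, but an analyst fills them in the ordinary way: everyone injected is accounted for, and observed NPRS and PGIC are summarised at each call with the number observed. Replacement adds no bias. If injected subjects were replaced, the expected number injected would be 26.4 to 30.0 at 10% to 20% dropout, and the safety denominator would show it.

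Missing scores could move the Week-12 mean by 0.1 to 0.6 points in an unknown direction, at most about 1.3 standard errors without replacement. No wording of Section 10.3 or 12.1 would remove that. The one substantive analysis that could be added is further off than the observed mean when dropout is unrelated to response or when good responders leave.

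This rests on the assumed dropout, SD and gap, on the trial staying a single-arm descriptive pilot with no test or decision threshold, and on the report giving the number observed beside each summary. It would be different if the Week-12 mean were compared with a fixed success criterion.
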